### Model Checking & Diagnostics

Bayesian Method (Primary):

- The Markov chain standard error (MCSE) should be compared to the standard deviation of the distribution (SD) to make sure that  $MCSE/SD \leq 0.01$  for all parameters in the mode.
- The Geweke diagnostic test will be used to check whether the mean estimates have converged by comparing means from the early and later part of the Markov chain using a z-score t-test. Large absolute values of the z-score statistic indicate rejection of the null hypothesis of no difference between the mean estimates obtained from the early and latter parts of the chain.
- Gelman & Rubin diagnostic checks should be used to assess if the Markov chains have mixed.
- Visual checks on diagnostic plots will be performed to assess:

- Has the Markov chain settled down?
- Are sufficient simulations being run?
- Is there sufficient burn-in?
- Is the effective sample size large enough?

Frequentist Method (Supportive):

- None.

### Model Results Presentation

Bayesian Method (Primary):

- The proportions of participants experience loss of asthma control on GSK3772847, Placebo and the ratio of GSK3772847/Placebo will be presented along with their 95% credible interval.

Frequentist Method (Supportive):

- The proportion of participants experiencing loss of asthma control on GSK3772847, Placebo and the odds ratio will be presented along with the 95% confidence intervals and p-value. This will be presented for all participants combined.

Fractional Polynomials (Exploratory Analysis):

- A plot of the relationship between the probability of experiencing loss of control on each treatment as well as the odds ratio versus continuous eosinophils will be produced.

## 7.2. Secondary Efficacy Analyses

### 7.2.1. Endpoint and Summary Measure

Endpoint	Summary Measure

Individual Components of Loss of Asthma Control:
 
 
• Proportion of participants with a <math>\geq 0.5</math> point ACQ-5 score increase from baseline.
 
• Proportion of participants who have pre-bronchodilator FEV1 decrease from baseline (measured at the end of Run-in) <math>> 7.5\%</math>.
 
• Proportion of participants where inhaled corticosteroids (ICS) cannot be titrated in accordance with the pre-defined schedule.
 
• Proportion of participants who have a significant asthma exacerbation (requiring OCS and/or hospitalisation).
 
• Proportion of participants with a clinically significant asthma exacerbation or inability to titrate ICS according to the pre-defined schedule
 
	
Number and percentage of participants experiencing each component of loss of asthma control (summary statistics only).

Time to loss of asthma control.
	
Mean, median, lower and upper quartiles of time to loss of asthma control, along with probability of experiencing loss of asthma control at each dosing visit.

The incidence, mean rate, and total number per participant of Asthma Related hospitalisations or Emergency Room (ER) visits during the study treatment period.
	
Summary statistics and study treatment exposure (no statistical analysis required).

Responders:
 
 
• Proportion of participants with <math>\geq 0.5</math> point ACQ-5 score decrease from baseline (responder) at each week from Week 1 to Week 16.
 
• Proportion of St. George's Respiratory Questionnaire (SGRQ) responders (at least a 4 unit improvement from baseline) at Weeks 4, 8, 12 and 16.
 
	
Number and percentage of participants (summary statistics only)

Change from Baseline Analysis:
 
 
• Change from baseline in pre-bronchodilator FEV1
 
• Change from baseline in fractional exhaled nitric oxide (FeNO)
 
	
Mean change from baseline (summary statistics only)

Endpoint	Summary Measure
Change from Baseline: 
 
• Change from baseline in ACQ-5 absolute score at each week from Week 1 to Week 16.
 
• Change from baseline in SGRQ total score at Weeks 4, 8, 12 and 16.
 
	Mean change from baseline (summary statistics only)

 
• Change from baseline in mean morning peak expiratory flow (PEF) and mean evening PEF for each four week period of the overall 16 week treatment period.
 
• Change from baseline in mean daytime asthma symptom score over each four weeks of the 16 week treatment period.
 
• Changes from baseline in night-time awakenings due to asthma symptoms requiring rescue medication use over each four weeks of the 16 week treatment period.
 
• Change from baseline in rescue medication use (albuterol/salbutamol): mean number of inhalations per day over each four weeks of the 16 week treatment period.
 
	Change from baseline (summary statistics only)

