**7.2.3. Strategy for Intercurrent (Post-Randomisation) Events**

For the analysis of time to loss of asthma control, both primary and secondary estimands (Section 7.1.4) will be examined. It is important to assess both estimands as data is missing after withdrawal or loss of asthma control. This could produce biased estimates, as loss of control and therefore missing data is related to study treatment, and so the secondary estimand where missing data is set as non-responders must also be considered.

For all other endpoints, only the primary estimand will be examined. This estimand uses all data as collected, except for data collected after the date of loss of asthma control or early withdrawal from study treatment.

Once participants experience loss of asthma control and/or withdraw from study treatment they immediately restart their standard of care medication (ICS/LABA). As a

result, any data collected past this point will have been impacted by the standard of care medications and any estimates produced biased by the additional use of ICS/LABA. For this reason, data post withdrawal from study treatment is not included in the on-treatment efficacy analysis.

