## 12.4. Appendix 4: Study Phases and Treatment Emergent Adverse Events

### 12.4.1. Study Phases

Assessments and events will be classified according to the time of occurrence relative to study treatment start date.

Study Phase for all data except efficacy	Definition
Pre-treatment	Date $\leq$ Study Treatment Start Date
On-treatment	Study Treatment Start Date < Date $\leq$ Study Treatment Stop Date + 28 days
Post-treatment	Date > Study Treatment Stop Date + 28 days

Study Phase for efficacy	Definition
Pre-treatment	Date $\leq$ Study Treatment Start Date
On-treatment	Study Treatment Start Date < Date $\leq$ Date of discontinuation from study treatment Or if the participant did not discontinue early from study treatment Study Treatment Start Date < Date $\leq$ Study Treatment Stop Date + 28 days
Post-treatment	Date > Study Treatment Stop Date + 28 days

Once participants withdraw from study treatment they immediately restart their standard of care medication (ICS/LABA). As a result, any data collected past this point will have been impacted by the standard of care medications and any estimates produced biased by the additional use of ICS/LABA. For this reason, data post withdrawal from study treatment is not included in the on-treatment efficacy analysis.

The post treatment definition is the same for efficacy and safety analysis.

Completion of study epoch's will be defined as the following:

Study Phase	Definition of Completion
Run-in	Randomised into study and received first dose of study treatment
Treatment	Completed Week 16 visit or withdrew from treatment phase due to loss of asthma control
Follow up	Completed 12 week follow-up period

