### 12.6.2. Study Population

Age
Date of birth will be set as PPD YYYYY where YYYYY is the year of birth taken from the CRF. For participants who attended a screening visit, age will be calculated at the screening visit date. For pre-screen failures, age will be calculated at the pre-screening visit date.
Body Mass Index (BMI)
BMI = Weight (kg) / Height(m) 
Treatment Misallocations
To allocate treatment, the number of doses of GSK3772847 and Placebo that were given will be calculated, and the subject will be assigned to whichever treatment has the higher number. The only exception will be when both treatments were given equally, in which case the subject will be assigned their randomised treatment.
Early Withdrawal from Study Treatment Date

The eCRF captures the study treatment start and end, however this is the physical time and date of the infusion. The date of early withdrawal from study treatment is not captured and should therefore be calculated as follows:
 
 
• If the participant withdrew from treatment due to loss of asthma control then the date of early withdrawal from study treatment is set to the date of loss of asthma control.
 
• If the participant withdrew due to an AE/SAE/Death then withdrawal date is set to the AE/SAE onset date (all deaths should be reported as serious adverse events)
 
• If the participant withdrew from study treatment (for a reason other than those above) during the first 10 weeks of the study i.e. during the down titration of the background medications, then the FP/SAL or FP discontinuation date should be used as the date of withdrawal from study treatment.
 
• For participants who withdraw from study treatment (for a reason other than those above) between Week 10 and Week 16, there is no information on when they withdrew as they are no longer taking background medications. The date of early withdrawal from study treatment should therefore be set to the maximum of date of last dose of FP and date of last dose +1. This is because no more information is available other than the fact that they had not lost control prior to completing the down titration or prior to receiving their final dose of IP.
 

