**Extent of Exposure (Therapeutic Coverage)**

- IP is administered approximately every 4 weeks and each dose viewed as providing therapeutic coverage for 4 weeks (28 days).
- Number of days of exposure to study drug will be calculated based on the formula:  

$$\text{Duration of Exposure in Days} = \text{Study Treatment Last Dose Date} - (\text{Study Treatment First Dose Date}) + 29$$
- The only exception to this will be when a participant dies in which case  

$$\text{Duration of Exposure in Days} = \text{Death Date} - (\text{Study Treatment First Dose Date}) + 1$$

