

Rate of Events per 1000 Treatment Years
 
Rate of events per 1000 treatment years will be calculated using:
 
Rate = number of events * 1000 / total treatment exposure in years where subjects can contribute more than one event.
 
This is equivalent to: Rate = number of events * 1000 / (number of subjects in treatment group * mean treatment exposure in years).

--

Maximum/Minimum Definitions for Vital Signs Data
 
Maximum and Minimum: Maximum and Minimum post-randomisation value over all time-points (including scheduled and unscheduled assessments) will be presented.

---

FEV1

Absolute Reversibility
 
Absolute reversibility (mL) = (post-bronchodilator FEV1 – pre-bronchodilator FEV1)

Percent Reversibility
 
Definition of Percentage Reversibility as a percentage of predicted FEV1 = ((post-bronchodilator FEV1– pre-bronchodilator FEV1) / predicted FEV1) x 100%
 
Definition of Percentage Reversibility as a percentage of pre-bronchodilator FEV1 = ((post-bronchodilator FEV1– pre-bronchodilator FEV1) / pre-bronchodilator FEV1) x 100%

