## 12.10.5. Efficacy Tables

Efficacy: Tables					
No.	Population	IDSL / Example Shell	Title	Programming Notes	Deliverable [Priority]
Exposure					
2.1.	SAFF_ALL	EX1	Summary of Exposure to Study Treatment	ICH E3	ETP, SAC
Primary Endpoint: Loss of Asthma Control Weeks 0-16					
2.2.	mITT_LoC	EFF_T01	Summary of Loss of Asthma Control	Include overall loss of control, each component and the combination of exacerbation or inability to titrate.	ETP, SAC
2.3.	mITT_LoC	EFF_T02	Summary of On-treatment Intercurrent Events		ETP, SAC
2.4.	mITT_LoC	EFF_T03	Bayesian Analysis of Loss of Asthma Control Over Weeks 0-16 (Primary Estimand)		ETP, SAC
2.5.	mITT_LoC	EFF_T04	Frequentist Analysis of Loss of Asthma Control Over Weeks 0-16 (Primary Estimand)		ETP, SAC
2.6.	mITT_LoC	EFF_T03	Bayesian Analysis of Loss of Asthma Control Over Weeks 0-16 (Secondary Estimand)		ETP, SAC
2.7.	mITT_LoC	EFF_T04	Frequentist Analysis of Loss of Asthma Control Over Weeks 0-16 (Secondary Estimand)		ETP, SAC
Secondary Endpoint: Loss of Asthma Control Weeks 0-6					
2.8.	mITT_LoC	EFF_T03	Bayesian Analysis of Loss of Asthma Control Over Weeks 0-6 (Primary Estimand)		ETP, SAC
2.9.	mITT_LoC	EFF_T04	Frequentist Analysis of Loss of Asthma Control Over Weeks 0-6 (Primary Estimand)		ETP, SAC
2.10.	mITT_LoC	EFF_T03	Bayesian Analysis of Loss of Asthma Control Over Weeks 0-6 (Secondary Estimand)		ETP, SAC

Efficacy: Tables					
No.	Population	IDSL / Example Shell	Title	Programming Notes	Deliverable [Priority]
2.11.	mITT_LoC	EFF_T04	Frequentist Analysis of Loss of Asthma Control Over Weeks 0-6 (Secondary Estimand)		ETP, SAC
Secondary Endpoints: Time to Loss of Asthma Control					
2.12.	mITT_LoC	EFF_T05	Summary and Analysis of Time to Loss of Asthma Control (Primary Estimand)		ETP, SAC
2.13.	mITT_LoC	EFF_T05	Summary and Analysis of Time to Loss of Asthma Control (Secondary Estimand)		ETP, SAC
Secondary Endpoints: Hospitalisation and Emergency Room Visits					
2.14.	mITT	EFF_T06	Summary and Rate of Asthma-Related On-treatment Hospitalisations and Emergency Room Visits (Primary Estimand)		ETP, SAC
Secondary Endpoint: ACQ-5 and SGRQ					
2.15.	mITT	EFF_T07	Summary of Raw and Change from Baseline in ACQ-5 Total Score (Primary Estimand)		ETP, SAC
2.16.	mITT	EFF_T07	Summary of ACQ-5 Responders (Primary Estimand)		ETP, SAC
2.17.	mITT	EFF_T07	Summary of Raw and Change from Baseline in SGRQ Total Score (Primary Estimand)		ETP, SAC

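### The hospitalisation/ER rate in Table 2.14 counts events only to loss of control, but the plan's only exposure definition runs to last dose plus 28 days

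*SAP*

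**What the plan says.** Section and table numbers are those of the amended plan.

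**Endpoint.** Section 7.2.1 lists "The incidence, mean rate, and total number per participant of Asthma Related hospitalisations or Emergency Room (ER) visits during the study treatment period", with the summary measure "Summary statistics and study treatment exposure (no statistical analysis required"). The display is Table 2.14, "Summary and Rate of Asthma-Related On-treatment Hospitalisations and Emergency Room Visits (Primary Estimand").

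**Which events count.** For every endpoint except time to loss of control, 7.2.3 examines only the primary estimand, which uses all data "except for data collected after the date of loss of asthma control or early withdrawal from study treatment". Section 12.4.1 agrees: "data post withdrawal from study treatment is not included in the on-treatment efficacy analysis". Its efficacy window closes at discontinuation for those who stop early, and at last dose plus 28 days only for the others. When the reason is loss of control, 12.6.2 fixes the date: "then the date of early withdrawal from study treatment is set to the date of loss of asthma control".

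**What the plan offers as a denominator.** Section 12.6.2 defines exposure as last dose date minus first dose date plus 29 days, with "each dose viewed as providing therapeutic coverage for 4 weeks (28 days"). Death is the only exception. The only rate formula is in 12.6.4, under Safety. It divides the number of events, times 1000, by "total treatment exposure in years where subjects can contribute more than one event".

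**The concern.** The events and the person-time cover different periods. After loss of control or early withdrawal, a participant can no longer add an event to Table 2.14. Under 12.6.2, that participant still adds exposure days until 28 days after the last dose. A denominator longer than the period in which events can count lowers the rate.

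The mismatch falls on the participants most likely to have events, because an exacerbation needing hospitalisation is itself a criterion for loss of control (section 2.3). What is at stake is the accuracy of one descriptive rate for a named secondary endpoint.

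**Working it through.** **Inputs from the SAP**
- Doses at Weeks 0, 4, 8 and 12, i.e. Days 1, 29, 57 and 85 (2.4 and the schedule in 12.2.1).
- A completer's treatment period is 113 days (7.2.4.1).
- Loss of control is 44% on placebo and 28% on GSK3772847 (2.6). The 28% is the proportion paired with the minimum detectable effect, not a forecast.

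**Assumptions not in the SAP**
- The timing of losses, taken as the same in both arms.
- Doses are given on schedule, with none on the day control is lost.
- Everyone who keeps control contributes 113 days.
- Day 1 is treated as countable. Section 12.4.1 puts the start date in the pre-treatment phase, but that one day applies to everyone and is ignored.

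**Plan's own figures.** Exposure for a completer is 85 − 1 + 29 = 113 days, which matches the stated period, so the two windows agree for completers. The stated 36% effect also reproduces: 1 − 28/44 = 36.4%.

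**One participant who loses control**
- Day 8: exposure 1 − 1 + 29 = 29, countable 8, excess 21 days.
- Day 30, just after dose 2: exposure 29 − 1 + 29 = 57, countable 30, excess 27 days.
- Day 43: exposure 57, countable 43, excess 14 days.
- Day 29, 57 or 85 before the dose, or Day 113: excess 0.
- If the dose had been given on the day of loss, the excess would be 28 days (57 − 29).

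Withdrawals for other reasons behave the same way. After the Week 12 dose, 12.6.2 can date the withdrawal at last dose plus 1 day, leaving up to 27 excess days.

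**By arm.** Let p be the proportion losing control, r their mean countable days and e their mean exposure days.

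Understatement = 1 − [p·r + (1 − p)·113] / [p·e + (1 − p)·113]

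For losses spread evenly over Days 2 to 113, r = (2 + 113)/2 = 57.5 and e = (29 + 57 + 85 + 113)/4 = 71.0.
- Placebo: countable 0.44 × 57.5 + 0.56 × 113 = 88.6; exposure 0.44 × 71.0 + 0.56 × 113 = 94.5; understatement 6.3%.
- GSK3772847: countable 0.28 × 57.5 + 0.72 × 113 = 97.5; exposure 0.28 × 71.0 + 0.72 × 113 = 101.2; understatement 3.7%.

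| Assumed timing of losses | r | e | Placebo | GSK3772847 |
|---|---|---|---|---|
| Even, Days 2–113 | 57.5 | 71.0 | 6.3% | 3.7% |
| Weekly ACQ-5 days | 60.5 | 71.0 | 4.9% | 2.9% |
| Clinic visits, Weeks 4–16 | 71.0 | 77.0 | 2.7% | 1.6% |
| Weeks 6, 10 and 14 only | 71.0 | 85.0 | 6.1% | 3.7% |
| Days 30–71 | 50.5 | 66.3 | 7.5% | 4.4% |
| Days 2–43 | 22.5 | 38.3 | 8.7% | 4.8% |
| Pre-dose at dosing visits, or Day 113 | 71.0 | 71.0 | 0% | 0% |

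These are the patterns tried, not bounds. Losses bunched in the first days after a dose would give more.

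**The case against.** The strongest objection is that the denominator is inferred. Section 7.2.1 names exposure but does not say that events are divided by it. The exposure formula sits under Study Population and the rate formula under Safety. The efficacy derivations in 12.6.3 contain no rate, and the mock shells are available only on request. A mean rate could also be built per participant. This stands as far as it goes: the plan does not spell out the division for Table 2.14. But it gives no other definition of exposure or of an event rate, so a programmer working from it would arrive at the mismatch.

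A reader might also infer that the rates are certainly too low, always more so on placebo, and that the drug's benefit is therefore diluted. The documents do not support that. The error is zero if losses are identified pre-dose at dosing visits or on Day 113. The gap between arms needs more losses on placebo with similar timing in both arms. A reader dividing the two displayed rates would find the ratio moved by about 0.963/0.937 = 1.03 under even timing, but the plan calculates no such ratio, interval or test.

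The effect is also small for this kind of table. A 6.7% difference in person-time (94.5/88.6) matters less than one event unless an arm has more than about 1/0.067 ≈ 15 events. That is a fair reason for low priority, but it does not make the two periods agree.

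**Conclusion.** Wrong as written, low severity. The event cut-off is explicit in 7.2.3, 12.4.1, 12.6.2 and the title of Table 2.14. The plan's only exposure and rate definitions do not stop there. If they are applied with doses on schedule, the descriptive rate is understated or at best unchanged. The size is about 6% on placebo and 4% on GSK3772847 for evenly spread losses, and 0 to 8.7% and 0 to 4.8% over the other timings tried. These figures rest on 44% v 28% loss of control, common timing in both arms, and use of the 12.6.2 exposure formula as the denominator.

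Incidence and total number per participant do not use person-time and are unaffected, as is the primary analysis.

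**What to change.** In 7.2.1 or 12.6.3, define person-time for Table 2.14 as first dose to the earliest of loss of control, early withdrawal from study treatment, death, or last dose plus 28 days. State that events are counted to the same end date and divided by this person-time. Keep the 12.6.2 formula for the exposure table, where it serves its own purpose. Counting events over the whole exposure period would also align the two, but it would depart from the primary estimand in 7.2.3.

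The cost is one derived variable, built from dates the plan already derives or collects. Displayed rates would change by a few per cent.

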**7.2.2. Population of Interest**

The secondary efficacy analyses will be based on the modified Intent to Treat population, unless otherwise specified.

**7.2.3. Strategy for Intercurrent (Post-Randomisation) Events**

For the analysis of time to loss of asthma control, both primary and secondary estimands (Section 7.1.4) will be examined. It is important to assess both estimands as data is missing after withdrawal or loss of asthma control. This could produce biased estimates, as loss of control and therefore missing data is related to study treatment, and so the secondary estimand where missing data is set as non-responders must also be considered.

For all other endpoints, only the primary estimand will be examined. This estimand uses all data as collected, except for data collected after the date of loss of asthma control or early withdrawal from study treatment.

Once participants experience loss of asthma control and/or withdraw from study treatment they immediately restart their standard of care medication (ICS/LABA). As a

result, any data collected past this point will have been impacted by the standard of care medications and any estimates produced biased by the additional use of ICS/LABA. For this reason, data post withdrawal from study treatment is not included in the on-treatment efficacy analysis.

**7.2.4. Statistical Analyses / Methods**

Details of the planned displays are provided in [Appendix 10: List of Data Displays](#) and will be based on GSK data standards and statistical principles.

Unless otherwise specified, endpoints / variables defined in Section 7.2.1 will be summarised using descriptive statistics, graphically presented (where appropriate) and listed.

**7.2.4.1. Statistical Methodology Specification**

Endpoint / Variables

 
Time to loss of asthma control.
 

Strategy for Intercurrent (Post-Randomisation) Events

 
Both primary and secondary estimands (Section 7.1.4) will be examined. It is important to assess both estimands as data is missing after withdrawal or loss of asthma control. This could produce biased estimates, as loss of control and therefore missing data is related to study treatment, and so the secondary estimand where missing data is set as non-responders must also be considered.
 

Model Specification

 
Time to loss of asthma control will be analysed on the Modified Intent-to-Treat excluding GCP non-compliant subjects (Loss of Control) population using Kaplan-Meier analysis (Proc lifetest). Within the Kaplan Meier plot participants will either be counted as an event or they will be censored.
 
A log rank test will be performed to test for difference between the time to loss of asthma control on Placebo compared with GSK3772847
 
 
Primary Estimand:
 
 
Events: Participants who experience loss of asthma control during the study
 
Censoring: Participants who discontinue investigational product for reasons other than loss of asthma control will be censored at the date of early withdrawal from study treatment. Participants who successfully complete the 16 week treatment period will be censored at 113 days (16 weeks + 1 day).
 
 
Secondary Estimand:
 
 
Events: Participants who experience loss of asthma control during the study or who discontinue investigational product for reasons other than loss of asthma control (date of event will be set to date of early withdrawal from study treatment).
 
Censoring: Participants who successfully complete the 16 week treatment period will be censored at 113 days (16 weeks + 1 day).
 

Time to event/censoring = Date of event/censoring – Treatment start date + 1. If participants experience multiple reasons for loss of control then the earliest date will be used as described in Section 0.

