### Model Results Presentation

- Kaplan-Meier plots of the probability of a participant experiencing loss of asthma control by treatment will be produced.
- In addition, a summary table will be produced showing the probability of experiencing loss of asthma control by 4, 8, 12 and 16 weeks along with the median, upper and lower quartiles of time to loss of asthma control on both treatment arms (this will be NA if <50% of participants on a treatment lose control).

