**12.3. Appendix 3: Assessment Windows**

**12.3.1. Definitions of Assessment Windows for Analyses**

Nominal visits will be used and no windowing will be applied for analysis.

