**12.6.3. Efficacy**

Loss of Asthma Control
Multiple Loss of Asthma Control

 
If a participant reaches loss of control for multiple reasons then all reasons will be reported. For any time to loss of asthma control analysis, the time of the earliest component of loss of control will be used.
 

Date of Loss of Asthma Control
Date of loss of control will be taken from the loss of control log page.

Diary Data

The vendor data captures the date on which the subject completes the diary (actual date of collection) rather than the date to which the questions relate. For example, in the morning diary subjects are asked ‘Did you wake up due to asthma symptoms’ and ‘when you woke up due to your asthma symptoms did you use any rescue bronchodilator?’ In the evening diaries subjects answer a question on daytime asthma symptoms and record the number of puffs of rescue medication used during the day. This means that the morning diary date in the raw data refers to the events during the previous night and that the evening diary relates to the events during the day time.
 
In order to ensure that correct observations are assigned to each four-week time period, measurements recorded in the morning diary will have 1 day removed in the analysis dataset to ensure that the date reflects the time period that the information related to. This adjustment is not required for evening diary as these are collected in the evening of the day to which they relate. Questions which this affects are those where the timepoint reference is MORNING:
 
 
Was evening dose taken?
 
Did you wake up due to asthma symptoms?
 
When you woke up due to your asthma symptoms did you use any rescue bronchodilator?
 
Number of puffs – night time
 
 
PEF assessments will not have the adjustment made as these reflect the PEF as assessed (so the PEF recorded in the morning diary is the PEF at that time).

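### Completers are censored at day 113 but an in-window Week 16 loss of control can be timed up to day 116, so one late event can end an arm's Kaplan-Meier curve at 100%; the single NA condition for the quantiles also needs splitting

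*SAP*

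**What the plan says.** For time to loss of asthma control, SAP Section 7.2.4.1 sets the censoring of completers under both estimands: "Participants who successfully complete the 16 week treatment period will be censored at 113 days (16 weeks + 1 day". Events are "Participants who experience loss of asthma control during the study" (the secondary estimand adds other discontinuations of study treatment), and no last day is given. Time is computed from dates: "Time to event/censoring = Date of event/censoring – Treatment start date + 1". Section 12.6.3 gives the source of the event date: "Date of loss of control will be taken from the loss of control log page".

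The schedule in Section 12.2.1 puts Visit 11 (Week 16) at study day 113 with a window of 3 days either side. Spirometry and the review of the loss-of-control criteria both take place there. Section 12.3.1 adds: "Nominal visits will be used and no windowing will be applied for analysis".

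Section 7.2.1 promises "Mean, median, lower and upper quartiles of time to loss of asthma control". The results paragraph of Section 7.2.4.1 lists the probabilities by 4, 8, 12 and 16 weeks and then the median and both quartiles, followed by one bracketed condition: "this will be NA if <50% of participants on a treatment lose control".

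**The concern.** Events and completers are placed on different time limits. A participant seen on day 115 who is found to have lost control has time 115. Every participant seen in the same window without loss of control has time 113, whatever the visit date. When the day-115 event is processed, the completers have already left the risk set, so the estimator treats the event as if it happened to everyone still under observation.

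The outputs at stake are the Kaplan-Meier plots (Figures 2.9-2.10) and the summary and analysis tables for this endpoint (Tables 2.12-2.13), including the mean, the quartiles, the 16-week probability and the log-rank test. A second, independent defect sits in the same tables. One 50% condition follows three quantiles, although each quantile becomes estimable at a different event proportion.

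**Working it through.** **Inputs.** 70 evaluable participants per arm, 44% loss of control on placebo and 28% on GSK3772847 (Section 2.6). Completer censoring at day 113. Visit 11 window days 110-116.

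**The plan's own figure.** With a pooled standard error, z = (0.44 − 0.28)/√(0.36 × 0.64 × 2/70) = 1.97, p = 0.049 (two-sided 5% assumed; the SAP states no alpha). The reduction is 1 − 0.28/0.44 = 36%. The minimum detectable effect reproduces. It is not in dispute and only supplies the planning rates.

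**Who is at risk after day 113.** Completers are not. Under Section 12.6.2, withdrawals between Weeks 10 and 16 for reasons other than loss of control or an adverse event are dated to the later of the last FP dose and the day after the last infusion, which falls well before day 113. Only a withdrawal dated by adverse-event onset could be later. Otherwise the risk set holds only participants with late-dated events, and at the last one S(t) is multiplied by (1 − 1/1) = 0.

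**Illustration.** 31/70 events on placebo and 20/70 on GSK3772847, one event in the arm dated day 115, the others spread over days 15-110 (illustrative; the jump does not depend on them):

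| Rule | Placebo | GSK3772847 |
|---|---|---|
| SAP, read at day 113 | 30/70 = 42.9% | 19/70 = 27.1% |
| SAP, at day 115 | 100% | 100% |
| Event time limited to day 113 | 31/70 = 44.3% | 20/70 = 28.6% |
| Completers censored at actual visit dates, spread over days 110-116 | about 48% | about 32% |

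**Log-rank test.** With one late event, on placebo only, chi-square is 3.20 (p = 0.074), identical to the value if that event had never occurred. With completers still at risk when it is counted, chi-square is 3.72 (p = 0.054).

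**How often the curve jumps.** Let p be the event rate, f the share of events first found at Week 16, and g the share of those dated after day 113. Ignoring the adverse-event exception, P(at least one late event in an arm) = 1 − (1 − p·f·g)^70. Neither f nor g is in the SAP. I take f = 5-15% and g from 10% to 3/7 = 43% (visits spread evenly over the seven window days).

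- Placebo: 1 − (1 − 0.44 × 0.05 × 0.10)^70 = 14%, up to 1 − (1 − 0.44 × 0.15 × 3/7)^70 = 87%.
- GSK3772847: 1 − (1 − 0.28 × 0.05 × 0.10)^70 = 9%, up to 1 − (1 − 0.28 × 0.15 × 3/7)^70 = 72%.

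**16-week probability read at day 113.** The expected value is p(1 − f·g). Placebo: 0.44 × (1 − 0.005) = 43.8% down to 0.44 × (1 − 0.0643) = 41.2%, against 44%.

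**Upper quartile.** If 35 to 52 of 70 lose control (50% to under 75%), the NA condition does not apply and the upper quartile is truly not reached, yet a jump prints one near day 115. The probability is the sum over k = 35 to 52 of P(K = k) × [1 − (1 − f·g)^k], with K binomial(70, p). This gives 3-17% of placebo arms and under 0.01% of GSK3772847 arms.

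**NA condition, read literally.** The lower quartile is estimable from 18/70 events (25% of 70 is 17.5). P(18 to 34 events) is 81% at a true 44% and 71% at 28%. In those arms the quartile exists but would be shown as NA.

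**The case against.** Several points can fairly be made for the plan.

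- **Size.** The frequency of the jump rests on two assumed inputs, and an even spread of visits over the window may overstate late visits. Dates come from the log page and the earliest component counts. Weekly ACQ-5 scores and exacerbations between visits may date many events before Visit 11. This stands as a caution about size, so a range is given. The mechanism needs only one late event per arm.
- **Nominal timing.** Section 12.5.2 uses planned times for derived parameters unless otherwise stated, and Section 12.3.1 uses nominal visits. One might infer that a Week 16 event is timed at day 113. Section 7.2.4.1 states otherwise, because its formula subtracts dates and the event date comes from the log.
- **On-treatment phase.** Section 12.4.1 ("Or if the participant did not discontinue early from study treatment") ends the efficacy phase 28 days after the last dose. With dose 4 on day 85 give or take 3, that end falls anywhere on days 110-116, so it supplies no common limit at day 113.
- **Stronger readings.** A reader might infer that a false median would be printed for GSK3772847. It would not. The NA condition covers the median on any reading, and the chance of at least 35/70 events at 28% is 0.008%. Nor would the tabulated 16-week probability read 100%. Read at day 113 it is slightly too low. The log-rank test is not inflated either; it ignores a late event that falls in one arm only.
- **The NA condition.** The singular pronoun may refer to the median alone. The superseded RAP bound in the same file tied NA to the median and listed separate 50%, 25% and 75% thresholds, which suggests a merging slip. So the lower-quartile loss is a consequence of the literal reading, not a settled intention. On either reading nothing guards the upper quartile.

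**Conclusion.** The censoring rule is wrong as written and should be fixed. A fully in-window Week 16 event can send an arm's curve to 100% in the last days of Figures 2.9-2.10, provided nobody in that arm is censored later. The probability of this, roughly 14-87% for placebo and 9-72% for GSK3772847, is only as good as the assumed share and dating of Week 16 events. The accompanying errors are a distorted mean, a 16-week probability up to about 3 points low on placebo, a late event lost to the log-rank test, and an occasional spurious upper quartile on placebo. The NA condition is ambiguous and unsuitable for two of its three quantiles.

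This does not rank higher because time to loss of control is a secondary endpoint. The primary Bayesian and supportive logistic analyses use the binary outcome and are untouched.

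**What to change.** In Section 7.2.4.1:

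1. Set the time of any loss of control recorded at Visit 11 to min(actual day, 113). It then ties with completers censored at day 113 and, by the usual convention, is counted before they leave the risk set.
2. State that the 16-week probability is read at day 113.
3. Apply NA separately: lower quartile if under 25% lose control, median if under 50%, upper quartile if under 75%.
4. Label the mean as restricted to day 113.

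Censoring completers at their actual visit dates is a weaker alternative. In the illustration it gives about 48% and 32% instead of 44.3% and 28.6%, because completers seen early in the window leave the risk set before events found later in it.

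The cost is a few sentences of text and a small programming change. A few event times are shortened by up to 3 days.
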